EMR documentation (primary outcome)	Review EMR to see if new documentation of ACP conversation, change in code status, or advance directive forms documented by physicians or mid-level providers exist.	Baseline & at 1, 6, and 12 months
Self-reported ACP conversation survey (primary outcome)	Quantitative and qualitative questionnaires to assess the self-reported completion of ACP conversations with outpatient clinicians and families as well as barriers/facilitators of this process.	At 1, 3, and 6 months

Heard and understood survey (secondary outcome)	A validated instrument for seriously ill patients to report how well they feel heard and understood about their wishes for end-of-life care. ³¹	Baseline & 1, 3, and 6 months
Quality of communication survey (secondary outcome)	A validated instrument to measure the quality of communication about end-of-life care. ³²	Baseline & at 1, 3, and 6 months
Healthcare utilization (secondary outcomes)	Review EMR to see # of urgent care visits, ED visits, hospitalizations, hospice visits, and outpatient visits.	At 6 and 12 months before and 1, 6, 12 months after enrollment
Mortality	Review EMR to determine patient's vital status.	At 1, 3, and 6 months
Qualitative benefits and obstacles of ACP conversations after ED GOAL (secondary outcome)	Semi-structured interviews to assess the benefits of ED GOAL and obstacles participants faced in completing more ACP conversations with their outpatient clinicians and loved ones after ED GOAL (see interview guide).	At 1, 3, and/or 6 months

- **Description of planned genetic research as applicable (e.g., specific description of whole genome sequencing, creation of immortalized cell lines or induced pluripotent stems cells, and sharing of genetic material with collaborators and central repositories as applicable, etc.)**
Not applicable.
- **Description of plans for return of research results as applicable (e.g., specific description of, rationale for, and process by which research results will be returned, including to whom, by whom, and when, etc.). Include plans for managing incidental findings as applicable.**
Not applicable.
- **Definition of primary and secondary outcomes/endpoints. Note that outcome measures should be quantifiable and measurable.**
Please see **Table 4** above.
- **Definition of study termination criteria, e.g., objective criteria for clinical worsening, lack of improvement, and/or unacceptable adverse events**

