Describe plans for statistical analysis, including:

- **Statistical methods/data analysis plan**

Aim 1 quantitative data analysis:

We will conduct an intention-to-treat analysis. Since the primary outcome is mean change in self-reported ACP engagement, we do not expect differences among patients who are admitted vs. discharged. For our secondary outcome, we suspect that there is a propensity of more ACP documentation in patients who are hospitalized and missingness in patients who are primarily cared for at outside institutions. We will plan to use regression in subgroup analysis for ACP documentation to account for hospitalization status. In addition, we will perform sensitivity analyses to account for clustering by individual outpatient clinicians, palliative care consultations, and cognitive impairment status. We will also perform sensitivity analyses for survey respondents (e.g., patients vs. caregivers). We will compare patient demographics by study arm to assess randomization using bivariable analyses (t-test for continuous variables and chi-square for categorical variables). The mean changes in ACP engagement (primary outcome) at one month will be compared by study arms to estimate effect sizes. Within arms, we will use a one-sample binomial exact test of proportions for categorical outcomes (e.g., EMR documentation), and Wilcoxon signed ranks test for ordinal outcomes (e.g., ACP Engagement Survey) at baseline, after the intervention at one month. A p-value of 0.05 will be the significance threshold. To address missing data, I will conduct a secondary analysis using linear mixed models at baseline and one month. For qualitative outcomes,

Aim 2 qualitative data analysis:

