We will conduct in-depth, semi-structured interviews with participants. We will explore the perceived benefits of the intervention as well as barriers to completing ACP conversations after leaving the ED. The interviews will be recorded and professionally transcribed. The transcripts will be analyzed to identify recurring themes that illustrate the qualitative benefits (e.g., how the intervention changed their lives) and barriers to completing ACP conversations (e.g., how attempted ACP conversations were unsuccessful). Transcripts will be analyzed by two trained researchers to ensure interpretive integrity and consistency per standard comprehensive qualitative analysis methods. We will use framework analysis as the analytic approach,³³ which allows the flexibility of incorporating *a priori* considerations as well as more emergent themes in the data. The coding structure will be collaboratively and iteratively developed by the research team and include both prefigured and emergent codes.³⁴ We will use an ethnographic data management software program, NVivo 10 (QSR International). If there are disagreements, the mentors/advisors and we will review the quotes and themes to discuss their meaning and to achieve consensus. We will follow the consolidated criteria for reporting qualitative research.³⁵

- **Power analysis (e.g., sample size, evaluable subjects, etc.)**

For Aim 1 (quantitative data):

While this pilot RCT study is not powered to detect statistically significant differences in the ACP outcomes, we will compare 1-, 3-, 6-month ACP outcomes in the intervention arm to the control arm to estimate the preliminary effect sizes. Our prior study demonstrated a mean patient-reported ACP engagement increased from 3.8 to 4.3 on a 5-point scale, corresponding to a moderate effect size of 0.50.³⁶ A conservative estimate of effect size is 0.25. We also expect that 10% of enrolled patients will die before completing all follow-ups. With a sample size of 60 patients per group, we would have 90% power to detect the difference using a 2-sided Fisher's exact test ($\alpha=0.05$). We plan to exclude patients who die before 6-month in the analysis.

For Aim 2 (qualitative data):

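### Section 9 claims 90% power with 60 per group in the same paragraph that says the trial is not powered, and the stated inputs do not give 90%

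*Combined protocol and SAP*

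**What the plan says.** The power analysis for Aim 1 (Section 9) begins: "While this pilot RCT study is not powered to detect statistically significant differences in the ACP outcomes". It then cites a rise from 3.8 to 4.3 on a 5-point scale in a prior study, calls this an effect size of 0.50, and adds: "A conservative estimate of effect size is 0.25". It expects 10% of patients to die before completing follow-up. It then says: "With a sample size of 60 patients per group, we would have 90% power to detect the difference using a 2-sided" Fisher's exact test at alpha 0.05. The last sentence is: "We plan to exclude patients who die before 6-month in the analysis".

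The statistical methods for Aim 1, also in Section 9, define the main comparison: "The mean changes in ACP engagement (primary outcome) at one month will be compared by study arms to estimate effect sizes". They add: "A p-value of 0.05 will be the significance threshold". The hypothesis in Section 2 predicts a significant increase over usual care, on a composite of patient-reported and EMR outcomes. The measures table in Section 6 also lists "EMR documentation (primary outcome)" and "Self-reported ACP conversation survey (primary outcome)", both of which can be analysed as yes/no outcomes, whereas Section 9 treats documentation as secondary.

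The only event rates in the documents are in Section 1: 40% (20/50) with a new documented ACP conversation and 26% (13/50) with new or changed forms. Both come from a one-arm feasibility study.

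**The concern.** The contradiction needs no calculation. Neither power statement is limited to a particular outcome, so they cannot both be true as written.

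The 90% also has no visible derivation. The named test is for two proportions, but the effect sizes just before it describe a score. No SD is given, so 0.50 could be a standardized effect or simply 4.3 − 3.8 in scale points. It is also a one-arm pre/post change, not a between-arm difference. Section 1 attributes the same 3.8-to-4.3 change to self-efficacy, which Section 6 lists as one of several processes in the survey; Section 9 attributes it to ACP engagement.

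What is at stake is how the result will be read. With 90% power, a non-significant result looks like evidence against a worthwhile effect. With about 27% power it says very little. The findings are meant to support an R01 proposal for a definitive trial, so readers need to know which statement holds.

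**Working it through.** **Inputs.** 60 per arm (Section 2, Aim 1); two-sided alpha 0.05, effect sizes 0.25 and 0.50, and 10% deaths to be excluded (Section 9). Excluding deaths leaves 60 × 0.90 = 54 per arm; the text does not say whether 60 already allows for this.

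**1. Mean change, effects read as SD units (an assumption).** For a two-sample t-test, the noncentrality is d × √(n/2) with 2n − 2 degrees of freedom.
- n = 60, √30 = 5.477: d = 0.25 gives 1.369 and power 27.4%; d = 0.50 gives 2.739 and power 77.5%.
- n = 54, √27 = 5.196: d = 0.25 gives 1.299 and power 25.1%; d = 0.50 gives 2.598 and power 73.1%.

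The normal approximation at n = 60 agrees: Φ(1.369 − 1.960) = 27.7% and Φ(2.739 − 1.960) = 78.2%.

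For 90% power, n per arm ≈ 2 × (1.960 + 1.282)² / d², or about 336 at 0.25 and 84 at 0.50. The t-based figures are 338 and 86. Conversely, 60 per arm gives 90% power for about 0.60 SD, and 54 per arm for about 0.63 SD.

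**2. Mean change, effects read as raw scale points.** Then d = difference / SD, and the SD must be assumed. For a raw 0.25 at n = 60:

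| Assumed SD | Power |
|---|---|
| 1.0 | 27% |
| 0.7 | 49% |
| 0.5 | 78% |

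Reaching 90% at n = 60 needs an SD of the analysed change of at most 0.25 / 0.597 = 0.42 for a raw 0.25, or 0.50 / 0.597 = 0.84 for a raw 0.50. At n = 54 the limits are 0.40 and 0.79.

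**3. Fisher's exact test, 0.25 read as a 25-point difference.** Power by full enumeration, two-sided 0.05:

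| Control vs intervention | 60 per arm | 54 per arm |
|---|---|---|
| 1% vs 26% | 99.3% | 98.5% |
| 9% vs 34% | 90.0% | 85.9% |
| 15% vs 40% | 83.4% | 78.8% |
| 37.5% vs 62.5% | 74.7% | 66.0% |

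The first and third rows take the one-arm rates of 26% and 40% as the intervention rate and subtract 25 points. With this difference, 90% is reached only for control rates below about 9% or above about 66% at 60 per arm (below about 6% or above about 69% at 54).

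If the 25-point reading is dropped and 40% is kept as the intervention rate, 90% needs a control rate of about 13% or lower at 60 per arm, or just under 12% at 54. With 26%, it needs about 4.4% or 3.5% or lower. The documents give no control rate.

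**4. Precision.** The 95% CI half-width for the between-arm difference is t(0.975, 2n − 2) × √(2/n), which is 0.362 SD at n = 60 and 0.382 SD at n = 54.

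**The case against.** The strongest reply is that the 90% was quoted for Fisher's exact test, so t-test power answers a different question, and that 90% can be reached. It can: with 9% vs 34% or 13% vs 40% at 60 per arm, or with a small enough SD. It can also be reached for 0.50 if that is measured in baseline SD units and baseline and follow-up correlate at about 0.65. The SD of the change is then √(2 × 0.35) = 0.837, so d = 0.50 / 0.837 = 0.598 and power is about 90%. The 78% figure corresponds to a correlation of 0.5. This part stands: the 90% is unsupported, not disproved, and 27% and 78% hold only on the SD-unit reading. But every route needs an input the documents do not state, the correlation route is not a Fisher's test, and it would need a correlation above 0.9 to rescue 0.25.

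A second reply is that this is a pilot. Its power paragraph opens with the right disclaimer, the between-arm comparison is described as effect-size estimation, and the 0.05 threshold follows the sentence on within-arm tests. It is true that estimation is unaffected and that the threshold sentence alone does not prove a between-arm test is planned. The Section 2 hypothesis, however, does predict a significant between-arm increase, and the 90% claim invites that reading.

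**Conclusion.** The concern holds. The paragraph makes two opposite statements about what the trial can detect, names a test that does not fit the mean-change primary analysis, and gives a power figure that its own inputs do not produce. With the effects in SD units, power is 27% (0.25) and 78% (0.50) at 60 per arm, or 25% and 73% at 54, against the stated 90%. At the effect the plan calls conservative, a real difference would be missed about 73% of the time rather than 10%.

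These figures assume SD units for the analysed change, a two-sample t-test, and no loss other than deaths; survey non-response would lower them further. The contradiction and the missing control rate and SD do not depend on those assumptions. The sentence must be corrected because it is the plan's only numerical basis for 60 per group.

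**What to change.** In Section 9, delete the sentence claiming 90% power with Fisher's exact test and replace it with a statement matched to the primary analysis, for example:

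> With 54 to 60 evaluable participants per arm, the 95% confidence interval for the between-arm difference in mean change has a half-width of about 0.36 to 0.38 SD. Power is about 25 to 27% for a difference of 0.25 SD and 73 to 78% for 0.50 SD. The trial estimates effect size and is not a test of efficacy.

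Also:
- State that 0.50 comes from a one-arm pre/post change and equals 0.50 SD only if the SD is 1; give the SD if it is known.
- State whether 60 per group already allows for the 10% deaths, and what survey non-response is expected.
- Reconcile self-efficacy (Section 1) with ACP engagement (Section 9) as the source of the 3.8-to-4.3 change.
- If a Fisher-based figure is kept for a binary outcome, name the outcome and give both the control and intervention rates.
- Align the Section 2 hypothesis and the 0.05 threshold in Section 9 with the estimation purpose, so that the contradiction does not survive elsewhere.

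The cost is protocol wording and a less favourable stated figure. No patients are added, and neither conduct nor the planned comparison of mean changes is altered.

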Our intervention is followed by scheduled, follow-up visits at one, three, and six months afterwards. The follow-up visits will be performed to assess the outcomes as well as to serve as the ACP care navigation/coaching by our study clinician.

Study clinician training:

We will train the study clinicians to administer these tools by 3-hour didactic on the concepts of delirium, cognitive impairment, and dementia, as well as bedside practice administration with the PI until competency is demonstrated (PI will self-record the responses next to the study clinician administering the instrument and compare the results. We will repeat this process with new patient volunteers until there is no discrepancy). In the case of equivocal findings on these assessments administered by study clinician, the PI backup will be available.

Intervention fidelity:

To ensure that all study clinicians deliver our intervention consistently, we will check the intervention fidelity. The percent adherence to the intervention fidelity checklist will be measured for every participant encounter (see attached fidelity checklist). High fidelity will be defined as mean adherence of >70% to the components on the fidelity checklist, which is consistent with expert consensus for behavioral intervention studies.²⁸

- **Justification and safety information if FDA approved drugs will be administered for non-FDA approved indications (“off-label”): How are doses, routes of administration, or participant populations different from FDA approved indicated use?**

Not applicable.

- **Description of specific data variables to be collected, including data collection methods, assessments, data collection sheets, and/or schedule of assessments (A schedule/table of study assessments is preferred)**

Measures	Descriptions	Timing
ACP engagement survey for patients (primary outcome)	Used for patients , this validated instrument will measure the self-reported processes for ACP (knowledge, contemplation, self-efficacy, and readiness), and ACP behavior. ²⁹	Baseline & at 1, 3, and 6 months
ACP engagement survey for caregivers (primary outcome)	Used for surrogate decision-makers , this ACP engagement survey is validated to measure the same ACP processes and behaviors. ³⁰	Baseline & at 1, 3, and 6 months

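### The exclusion of patients who die before 6 months is not limited to 6-month outcomes; as written it conflicts with intention-to-treat and the 1-month primary comparison

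*Combined protocol and SAP*

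**What the plan says.** Section 9 (Statistical Analysis) of the combined protocol and SAP speaks to this in two places.

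- **Aim 1 quantitative data analysis.** The principle is stated without exception: "We will conduct an intention-to-treat analysis". The primary comparison is then set: "The mean changes in ACP engagement (primary outcome) at one month will be compared by study arms to estimate effect sizes". Aim 1 in section 2 uses the same one-month time point. A linear mixed model at baseline and one month is planned as a secondary analysis for missing data. Deaths are not mentioned.
- **Power analysis, Aim 1.** The paragraph says "we will compare 1-, 3-, 6-month ACP outcomes in the intervention arm to the control arm", then "We also expect that 10% of enrolled patients will die before completing all follow-ups", then gives power for 60 patients per group, and closes with "We plan to exclude patients who die before 6-month in the analysis".

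Section 6 (Study Procedures) gives the schedule: "Our intervention is followed by scheduled, follow-up visits at one, three, and six months afterwards". Its measures table includes a chart-based outcome ("Review EMR to see if new documentation of ACP conversation") and a vital-status review at 1, 3 and 6 months. Section 5 states that for moderate and advanced dementia the caregivers alone are the participants.

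**The concern.** Death before 6 months is a post-randomisation event, and death in months 2 to 6 comes after the primary outcome has been measured. Read as written, the rule discards an observed 1-month result because of something that happened later. The patient's chart documentation, which can be read up to death, goes with it. The 1-month comparison is then between 6-month survivors in each arm, not between the groups as randomised, and its analysis set cannot be settled until 6-month vital status is known.

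Two analysts could build different primary datasets from this plan. Deaths are expected: the plan allows for 10%, and one route to eligibility is that the ED clinician would not be surprised by death within 12 months. The pilot is not powered for significance, but section 1 says its findings will support a proposal for a definitive trial, so the set behind the effect sizes should be fixed beforehand.

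The rule also speaks only of patients. Where the caregiver is the sole participant, it does not say whether surveys the caregiver has already given are kept when the patient dies.

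**Working it through.** **Inputs from the documents.** 120 randomised, 60 per arm (section 2); 10% expected to die before completing all follow-ups (section 9); visits at 1, 3 and 6 months (section 6). I take the 10% to cover the period to the 6-month visit. The stated power plays no part in this check.

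**Number excluded.** 120 × 0.10 = 12, leaving 108 (54 per arm if deaths are balanced).

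**How many of these losses are avoidable.** A patient who dies before month 1 cannot give a 1-month survey under any rule. Only deaths after month 1 count. The documents do not time the deaths, so the avoidable loss is between 0 and 12.

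Under a constant hazard (an assumption):

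- deaths by month 1 = 120 × (1 − 0.9^(1/6)) = 2.1
- alive at month 1 = 120 − 2.1 = 117.9
- deaths in months 2 to 6 = 117.9 − 108 = 9.9

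**Effect on precision.** With balanced arms and an unchanged SD, the standard error (SE) of the arm difference is proportional to 1/√n. If x of the 12 deaths fall after month 1, the SE ratio (rule applied versus not applied) is √((108 + x)/108).

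| Deaths after month 1 (x) | SE ratio | Rise in SE |
|---|---|---|
| 0 | √(108/108) = 1.000 | 0% |
| 6 | √(114/108) = 1.027 | 2.7% |
| 9.9 (constant hazard) | √(117.9/108) = 1.045 | 4.5% |
| 12 | √(120/108) = 1.054 | 5.4% |

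For any given x these are upper figures, since they assume that everyone alive at month 1 completes the survey.

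**Bias.** In one arm, let q be the share of 1-month respondents who die in months 2 to 6, S the mean 1-month change of 6-month survivors, and D that of later decedents. The mean of all respondents is (1 − q)S + qD, and the rule reports S, so the arm mean shifts by q(S − D). The arm difference is therefore biased by

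q₁(S₁ − D₁) − q₀(S₀ − D₀).

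This is zero if q and S − D are the same in both arms. Under constant hazard q = 9.9/117.9 = 0.084 overall. The documents give neither q nor S − D by arm, so neither the size nor the direction of any bias can be derived.

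For scale only, suppose q = 0.084 in both arms and S − D differs between arms by an assumed 0.5 points on the 5-point scale. The bias is 0.084 × 0.5 = 0.04 points. An assumed 1.0 point gives 0.08. The prior study's change was 4.3 − 3.8 = 0.5 points.

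**The case against.** The strongest reply is that this is loose placement, not a real conflict. The sentence is not in the analysis text. It closes a paragraph under the heading "Power analysis (e.g., sample size, evaluable subjects, etc.)", shortly after the mortality allowance, so it may be a remark about evaluable numbers or 6-month outcomes. That reading is plausible, but nothing in the documents states it. The sentence is worded as an analysis rule, the paragraph names the 1-month outcome, and the power statement uses 60 per group rather than a reduced evaluable number.

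Second, the 10% might cover 12 months, since chart reviews run that far. With a constant hazard there would then be 120 × (1 − 0.9^(1/2)) = 6.2 deaths before month 6 and 120 × (1 − 0.9^(1/12)) = 1.05 before month 1, so about 5.1 between. The SE ratio would be √(118.95/113.84) = 1.022, a 2.2% rise. This is the less natural reading because the follow-up visits end at 6 months, and 2.2% lies within the range already given.

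Third, the effect is modest in a pilot not powered for significance. That stands for precision. It does not justify conditioning a randomised comparison on a later event when the remedy is one sentence.

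Fourth, the planned mixed model might recover these patients. It has no rule for deaths, and a patient excluded from the analysis would not enter it.

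The caregiver point is secondary, since the power paragraph uses patients as shorthand throughout, but it still needs a line.

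**Conclusion.** The concern holds: the sentence is wrong as written and should be fixed. No text limits the exclusion to 6-month outcomes, labels it a sensitivity analysis or defines a modified intention-to-treat set. Applied literally, it contradicts the stated intention-to-treat principle and removes valid 1-month data from the primary comparison.

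About 12 of 120 patients are affected at the plan's own mortality figure. How many of them have a usable 1-month survey depends on when deaths occur, which the documents do not say. The loss of precision is modest even at its upper limit. The main issue is validity, and there the harm may be nil or real. Confidence is high that the scope is unstated and that the literal rule is unsuitable. Which reading was intended cannot be told from the text.

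**What to change.** Replace the closing sentence of the Aim 1 power paragraph, and put the rule in the Aim 1 analysis text, along these lines:

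> Randomised participants are analysed in their assigned arm. The 1-month comparison includes everyone with a 1-month assessment, regardless of later death. Data collected before death at any visit are retained, including EMR documentation up to death. Survey results at each visit are described as among those alive, with deaths reported by arm. Caregiver surveys collected before the patient's death are retained.

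The secondary mixed model should follow the same set and say how patients who die before month 1 are handled. An analysis restricted to 6-month survivors may stay as a labelled sensitivity analysis. If only the 6-month outcomes were ever meant, this wording simply records that.

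The cost is small: one replaced sentence, slight extra analysis work, and noting the date of death during the vital-status review already planned at 1, 3 and 6 months. The date helps to define the EMR window.
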